Based on the foregoing review, this study will: 1) include a sample of dementia carers that include caregivers (in-home), care partners (with a facility), and caretakers (bereaved) who have recently (within six months) transitioned into a new phase of their caregiving career; 2) examine the effects of two self- management interventions delivered to carers based on their need (cut score) or preference in comparison with an attention control condition; 3) explore differences in carers at the three phases of the caregiving career on caregiver responses to their recent transition and health outcomes over time; and 4) control for the effects of number of months in carer role, dementia symptom severity, and caregiving demands. As such, this will be the first study to investigate self-management interventions across all three phases of the caregiving career of dementia carers.

Inclusion and Exclusion Criteria

Directions: Describe how individuals will be screened for eligibility. Using the tables below, describe the inclusion and exclusion criteria that will define who will be included and excluded in your final study sample.

Inclusion

1. At least 18 years old
2. Have a living family member, or a recently deceased family member diagnosed with Alzheimer's disease or another dementia
3. Identify self as a primary caregiver
4. In-home **Caregivers**: must be currently providing a minimum of 4 hours per day of supervision/direct care, and have entered that role within the past six twelve months;

Care partners whose family member moved into a nursing or assisted living

HRP-503SBER	TEMPLATE: SBER Protocol		
Approved:	01/2019	Prior Version:	05/2018

facility within the past ~~six~~ twelve months, and must report visiting their care recipient at least once per week (or have similar involvement with COVID-19 restrictions).

Caretakers (i.e. bereaved) whose family member is deceased within the past ~~six~~ twelve months, and are persons with direct oversight of the deceased person's belongings, estate, finances, etc., and/or while their family member was alive, did they consider yourself a primary caregiver (whether care recipient was at home or in a facility).

5. Be capable of performing informed consent and participating in study procedures

Exclusion

1. Does not have family member with Alzheimer's disease or another dementia

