The data collection for caregivers sampled involves three structured face-to-face sessions with data collectors, each lasting typically 60-90 minutes. Data will be collected at baseline (T1), at 4-6 months (T2) after the 4-week intervention, and at 12-4-6 months later (T3). The data collection includes measures of carer health conditions, carer life events, health rating of care recipient, resourcefulness (including financial resourcefulness), dementia symptom severity, caregiving demands, carer responses to perceived stress, depressive cognitions, negative emotions, carer health outcomes, caregiving effort scales, and COVID-19 questions comprising the 158-225 item questionnaire (bereaved caretakers are not asked all study measures since they are no longer actively caring for their family member). Demographic information will also be collected (e.g. occupation, annual income, education, and questions about the care recipient such as age, number of years diagnosed with dementia, specific diagnoses, and questions related to the participant's caring of their family member with dementia). The third, and final, data collection session involves the additional measure of an Intervention Evaluation Questionnaire that will ask participants for feedback regarding the intervention they received.

The table below shows which study instruments are administered at each time point:

Data Collection Instrument	Baseline / T1	4-6 months post-intervention / T2	12-4-6 months post-T2 / T3
Demographic and Descriptive Data*	X	X	X
Health Rating of Elder Care Recipient**	X	X	X
Cultural Justification for Caregiving	X	X	X
Resourcefulness Scale	X	X	X
Financial Resourcefulness	X		
Revised Social Readjustment Rating Scale	X	X	X
Revised Memory and Behavior Problems Checklist**	X	X	X
Perceived Stress Scale	X	X	X
Depressive Cognition Scale	X	X	X
Negative Emotions Checklist	X	X	X
Caregiver Appraisal of Functional Capacity**	X	X	X
Health Risk Behavior Scale	X	X	X
PROMIS Global Health Measures	X	X	X

HRP-503SBER	TEMPLATE: SBER Protocol		
Approved:	01/2019	Prior Version:	05/2018

Caregiving Effort Scales	X	X	X
Financial Stress	X		
COVID-19 Questions	X	X	X
Intervention Evaluation Questionnaire			X
Heart Rate Variability	X	X	X

* Questions 7-13 of the Demographics will NOT be asked to caretakers.

** These scales will NOT be asked to caretakers.

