INTERVENTION: Within two weeks of the first data collection session (including study scales and HRV data collection), carers within each of the three caregiving phases (caregivers, care partners, and caretakers) will be randomly assigned using a computer program to one of three treatment groups: 1) Self-management (SM) need, 2) Self-management (SM) preference, or 3) attention control. The SM-need group will receive a self-management intervention tailored to meet their need for resourcefulness training (RT) or biofeedback (BF) as

HRP- 503SBER	TEMPLATE: SBER Protocol		
Approved:	01/2019	Prior Version:	05/2018

determined by whichever baseline cut score is lower, the Resourcefulness Scale or the SDNN parameter for age and gender. Carers randomly assigned to the SM-preference will choose to do RT or BF according to their personal preference. However, we will use minimization methods for group assignment to ensure equivalent representation across the three treatment groups, and factors likely to affect variables of interest, including carer age, gender, and race/ethnicity, in order to insure demographic similarity.

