Prior to testing the study aims, demographic profiles for caregivers, care partners, and caretakers will be created through univariate descriptive statistics, including means, standard deviations, and range of scores, and will be used to assess continuous data; frequencies and percentages will be used to describe categorical data. We will track the health conditions and the life events of all carers and dementia symptoms, level of care, and health rating of the care recipient for those who are not bereaved. However, the primary aim (**Aim 1**) is to test the effects of health self-management interventions (RT or BF) delivered based on need (i.e., cut score) or preference (i.e., personal choice) of dementia carers who have transitioned within six months to a new phase in the caregiving career (to at-home caregiver, to care partner with a facility, or to caretaker following the death of care recipient). **Aim 1** is to compare carers who are randomly assigned to the need (SM-need, preference (SM-preference) group, or an attention control condition over 3 time points (baseline, 6 months, and 12 months) on carer responses (i.e., perceived stress, depressive cognitions, and negative emotions) (**Aim 1a**), and health outcomes (health risk, and physical and mental health) (**Aim 1b**). **Aim 2** will focus on comparing caregivers, care partners, and caretakers. For **Aims 2a and 2b**, we will determine whether differences exist among caregivers, caregivers, care partners, and caretakers in carer responses (**2a**) and health outcomes (**2b**) over time. For all analyses, we will control for the effects of three covariates: months in caregiver, care partner, or caretaker role, dementia symptom severity, and caregiving demands.

For both study aims, we will use a 3 group by 3-time point Repeated Measures Analysis of Variance (RMANOVA), as well as 3 group by 3-time point Repeated Measures Analyses of

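### Aim 2 compares three non-randomised caregiving phases without adjusting for carer age, gender or race/ethnicity, so the phase main effect can partly reflect demographic differences between phases

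*Combined protocol and SAP*

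**What the plan says.** **The comparison.** The Data Analysis Plan states that Aim 2 "will focus on comparing caregivers, care partners, and caretakers", on carer responses and health outcomes over time.

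**What is randomised.** In Study Design/Procedures, under Intervention, "carers within each of the three caregiving phases (caregivers, care partners, and caretakers) will be randomly assigned using a computer program" to a treatment group. Phase is thus a stratum within which assignment takes place. The same paragraph adds that "we will use minimization methods for group assignment to ensure equivalent representation across the three treatment groups", and extends this to "factors likely to affect variables of interest, including carer age, gender, and race/ethnicity, in order to insure demographic similarity".

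**The covariates.** The Data Analysis Plan fixes a single list that applies to both aims: "we will control for the effects of three covariates: months in caregiver, care partner, or caretaker role, dementia symptom severity, and caregiving demands". The closing paragraph of the Background gives the same list: the study will "control for the effects of number of months in carer role, dementia symptom severity, and caregiving demands". The RMANCOVA description also refers to the three covariates and adds none. It gives control of confounding as the purpose of the adjustment.

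**The sequence.** An unadjusted 3-group by 3-time RMANOVA comes first. The RMANCOVA follows only if that first step finds mean differences.

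**Demographics.** Gender, race and ethnicity are recorded at screening (Recruitment Methods, item 4). Under Data Collection, "Demographic information will also be collected (e.g. occupation, annual income, education" among other items. In the analysis, demographics by phase are used only for descriptive profiles.

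**The concern.** Whether a carer looks after someone at home, shares care with a facility or is bereaved depends on life circumstances. The three phases may therefore differ in age, gender and race/ethnicity. The protocol regards these as prognostic and balances them across arms, where random assignment already gives protection. It omits them from the comparison that has no such protection.

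If one phase is older, or includes more men, part of a phase difference in stress or in physical or mental health may be due to that composition. The opposite can also happen: a demographic imbalance could hide a real phase difference in the first step, and the adjusted step would then not be run. Aim 1 is not affected in this way, because treatment is randomised and minimised on these same factors.

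**Working it through.** **Text check.** Minimisation acts across treatment groups within phases, so it cannot balance one phase against another. None of the three listed covariates measures age, gender or race/ethnicity. No sentence adds a demographic term to the Aim 2 model. The descriptive profiles would show an imbalance but would not remove it, and no rule says what follows if one appears.

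**Inputs for an illustration.** The total of 350 is from the protocol (Recruitment Methods, item 5). The following are assumptions, because the documents do not give them:
- equal phases, so n = 350/3 = 116.7;
- two-sided alpha 0.05;
- correlation between visits 0.6;
- one demographic factor whose mean differs by d = 0.3 to 0.5 SD between two phases and which correlates r = 0.2 to 0.3 with the outcome;
- no true phase difference.

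The test is the phase main effect on the mean of three visits, without covariates, as in the planned first step. The plan states no error rate for this test, so there is no figure of its own to reproduce.

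**Spurious difference** = d × r: from 0.3 × 0.2 = 0.06 SD to 0.5 × 0.3 = 0.15 SD.

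**Variance of a three-visit mean** = (1 + 2 × 0.6)/3 = 0.733.

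**Pairwise contrast.** SE = √(2 × 0.733/116.7) = 0.112. The rejection probability is P(|N(bias/SE, 1)| > 1.96):
- 0.06/0.112 = 0.54, giving 0.083;
- 0.15/0.112 = 1.34, giving 0.267.

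**Planned 3-group test.** Place the middle phase halfway, so the phase means are 0, b/2 and b, with b = d × r. The sum of squared deviations is b²/2, and the noncentrality is 116.7 × (b²/2)/0.733:
- b = 0.06 gives 0.286; noncentral F(2, 347) rejects with probability 0.072;
- b = 0.15 gives 1.79; it rejects with probability 0.204.

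If two phases coincide and only the third differs, the range is 0.080 to 0.261.

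**Sensitivity.** A wider grid with visit correlation 0.5 and N = 350 gives, for the 3-group test:

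| d | r = 0.1 | r = 0.2 | r = 0.3 |
|---|---|---|---|
| 0.25 | 0.054 | 0.067 | 0.089 |
| 0.50 | 0.067 | 0.121 | 0.221 |
| 0.75 | 0.089 | 0.221 | 0.451 |

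With N = 280 (an assumed 20% loss) the range is 0.053 to 0.370.

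**Effect of adjusting.** In 4,000 simulated trials per setting (116 per phase), adding the factor as a covariate brought the rejection rate to 0.048 to 0.050 in all four settings tried. Without it, the rates in those settings were 0.054, 0.118, 0.221 and 0.461.

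**Limit.** These figures describe the test without covariates. They do not show how much bias would remain after the three planned covariates.

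**The case against.** **Aim 2 asks only whether differences exist.** The Background speaks of exploring differences, the only stated hypothesis belongs to Aim 1, and no causal effect of phase is claimed. On that reading an unadjusted difference is a correct descriptive answer, and it is a false positive only for a contrast standardised for demographics. This stands in part. The plan nevertheless adjusts Aim 2 and says that it does so to control confounding, so it is not purely descriptive. Reporting both estimates serves both readings.

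**A reader might infer that all of Aim 2 is compromised.** The documents do not support that. The plan also tests time by group and linear and quadratic trends. A demographic effect that is constant over visits cancels out of these and shifts only the phase main effect.

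**A reader might infer that the protocol says these factors do affect the outcomes, or that the phases are known to differ on them.** It says only that they are likely to affect variables of interest, and it gives no demographic data by phase. At d = 0.25 and r = 0.1 the rejection rate is 0.054. Several factors acting together could add up or offset each other.

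**A reader might want education and income as standing terms too.** The minimisation paragraph does not name them. T1 income is measured after the transition, and the Background notes that families bear out-of-pocket costs, so income may partly result from phase. Adjusting for it could remove part of a real difference. The data-collection table also says that demographic questions 7 to 13 are not put to caretakers, and the documents do not show which items these are.

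**Conclusion.** The point holds for the phase main effect in Aim 2. The closed covariate list leaves out carer age, gender and race/ethnicity, which the plan itself considers likely to matter and balances only across arms. Under the stated assumptions the spurious phase difference is 0.06 to 0.15 SD. The rejection rate is then about 7 to 20% for the planned 3-group test and 8 to 27% for a pairwise contrast, against a nominal 5%. These are illustrations: d, r, the visit correlation and equal phase sizes are not in the documents, and a small imbalance or correlation leaves the rate close to 5%. Time by phase is affected only if a demographic effect changes over time. The change should be made, but the gap does not invalidate Aim 2, and Aim 1 is not biased by it.

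**What to change.** 1. In the Data Analysis Plan, add T1 carer age, gender and race/ethnicity to the Aim 2 phase model as pre-specified standing terms. Fit that model whatever the unadjusted RMANOVA shows.
2. Report phase estimates with and without these terms.
3. Use education and income in a sensitivity analysis only, after confirming that both are recorded for caretakers.
4. State which instruments supply the symptom-severity and caregiving-demands covariates. The instrument table shows that the Revised Memory and Behavior Problems Checklist and the Caregiver Appraisal of Functional Capacity are not asked of caretakers. If these are the two covariates, as their content suggests, fit the three-phase demographic-adjusted model without them so that caretakers are not dropped.

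The cost is SAP wording, one additional model and a few of the 347 error degrees of freedom. No new data are needed for the three standing terms: gender, race and ethnicity are recorded at screening, and minimisation already requires age.

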CONSENT: At the first meeting, before the T1 interview begins, the data collector will confirm receipt of signed consent form (digital or paper). All research staff (including the project manager, data collectors, and interventionists) will be required to complete the "human subjects" training and obtain certification prior to entering the field for data collection or intervention. The consent form will explain the expectations of caregivers as research participants, risks they may encounter, benefits they may accrue, measures to be taken to maintain confidentiality, and voluntary nature of their participation. Potential study participants will be told they are being asked to participate in a study to examine method for helping family caregivers to self-manage their health. They will be told that they will be randomly assigned (using a computerized system) to one of the three study arms (Self-management need, self-management preference, or attention control). They will be told the study involves 3 face-to-face interviews with a trained data collector during which objective, validated questionnaires and HRV measures will be completed, as well as an intervention ("stress management method") between the first and second data collection interviews. The caregivers will be told that their confidentiality will be protected and that their names will not be revealed; results of the study will be reported in aggregate. They will be told that they are free to withdraw from the study at any point in time and that they do not need to supply responses to all questions posed on the study questionnaires. They will be told about the possible risk of feeling distressed while answering questionnaires or completing their daily logs, or using the biofeedback device (if applicable) and about measures that will be taken to minimize / manage the distress, including discontinuing participation and referral to mental health professionals if needed. They will be told that if a research team member, during a data collection or intervention meeting or call, suspects or witnesses any signs of elder abuse, neglect, or exploitation, a report will be filed with the county department of job and family services in compliance with Ohio law. They will be told about the potential benefit of stress reduction. Finally, they will be told that they will receive an incentive of a gift card valued at \$20 at Time Point 1 (T1), \$25 at T2, and \$30 at T3. In addition, they will receive \$20 for completing the face-to-face or virtual intervention session and \$5 for each week of completion of the progress log (up to 4 weeks or \$20). Participants will receive up to \$115 for completing all study activities.

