
DATA COLLECTION: Following informed consent, research staff will collect detailed contact information and schedule the first data collection session. During the COVID-19 pandemic, data collection will be completed verbally over the phone and/or electronically (emailed survey, video chat) using REDCap. For phone or video data collection, an email will be sent, if possible and requested, to participants with the answer response choices for each survey (this can also be sent by mail). If we are using phone for data collection, the Research Assistant (RA) will ask the participant each question and record the responses in our REDCap Surveys project. If collecting data using Zoom video, the RA will share the screen of the REDCap Surveys project, and record the answers for the participant as they review each survey question.

HRP-503SBER	TEMPLATE: SBER Protocol		
Approved:	01/2019	Prior Version:	05/2018

If neither of those two options are available for the participant (e.g., limited phone minutes, inability to use Zoom), and/or email is preferred, the study may email the REDCap surveys to study participants for them to complete on their own at an agreed upon date / time (similar to in-person appointment); in this instance, the RA can be available to answer questions or clarify information as needed, by phone or email. It may be that none of these options will work for a study participant, in which case we will consider that data “missed” if we cannot wait to collect the data in person at a later date (when we resume normal study activities). The precise method(s) will depend on the ability and resources of the study participant. We will contact active participants with Zoom/ phone instructions, by phone/text and/or email, as needed, and we will record the methods used for each data collection done remotely.

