Covariance (RMANCOVA) to control for the three covariates on carer responses (i.e., perceived stress, depressive cognitions, and negative emotions) (**Aim 1a and Aim 2a**) and health outcomes (health risk, and physical and mental health) (**Aim 1b and 2b**). We will use both analyses in a two-step process: first, we will use RMANOVA to determine if mean differences exist among the 3 groups over 3 time points. If we find mean differences, for the second step we will run RMANCOVA to identify how the covariates impact the initial findings. This controls for any confounding effects of the covariates on the repeated measures models and will also allow us to determine how much of an impact the covariates have on carer responses and health outcomes.

The RMANOVA and RMANCOVA will allow us to not only assess mean differences across time, group differences, and the interaction of time X group in order to test the trend of the means over time across the SM- need, SM-preference, and attention control condition in **Aim 1** and caregiver vs. care partner vs. caretaker in **Aim 2**. The RMANOVA and RMANCOVA not only can be used to determine if there are mean differences across the three time periods, but can also utilize orthogonal polynomial contrasts to determine whether linear and quadratic trends of the means across time are significant.

Confidentiality of Data

1. To maintain the confidentiality of the data:

I will use a unique study identifier to code individuals' identifiable data and will store the master list separate from the study data..

Other (please explain)

Provide a plan to destroy identifiers including how and when.

Identifiers in the Screening log (Box.com) and Contact Form (REDCap and CWRU BOX) will be destroyed after data collection is complete, and before the study is closed, by deleting the files.

How are you storing your electronic data?

UH Redcap

CWRU Redcap

Secure Research Environment (SRE)

CWRU Box

OnCore

UH Secure Network Drive

CWRU Secure Network Drive

Other - List storage method and provide justification:

2. Storage location of the paper research data and documents, if applicable:

Paper research data and documents will be stored in a double-locked secure environment in the following location:

France Payne Bolton School of Nursing – Health Research Campus study office

3. Will data be shared?
 Yes
1. List the exact data elements that will be shared:
2. Describe how data will be sent:
 No
 N/A

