There is potential benefit to research participants.

Describe the potential benefits that individual research participants may experience from taking part in the research. Include the probability, magnitude, and duration of the potential benefits.

There is no direct benefit to research participants.

If no direct benefit, state the potential benefit to society or others. *Do not list compensation.*

Withdrawal of Research Participants

Directions: Describe the anticipated circumstances under which research participants will be withdrawn from the research without their consent. Also include the procedures that will be followed when a research participant withdraws or are withdrawn from the research, including partial withdrawal from procedures with continued data collection.

N/A

Participants have the option of withdrawing from the study at any time and can request that no further information be shared about them from that point on. If a study participant withdraws consent to participate in the study, a research team member will notify the project manager to complete end of study documentation.

The project manager will review cases regularly with research staff to determine which study participants should be withdrawn from the study. Research participants will be withdrawn from the research without their consent if they are non-responsive to phone calls, emails, texts, or letters and considered lost to follow up.

Data that were collected prior to a study participant's withdrawal will be de-identified and still be used in the data analysis for the study. After withdrawal, no further data will be collected for that participant.

Alternatives to Participation

Directions: List other options to participation. If subjects will be compensated with extra course credit, the course instructor offering extra course credit must provide alternatives to earn extra course credit. The alternative assignment must require equal or less time and effort for the same amount of earned extra credit that you can earn through participation in research. If there are other available clinical treatments, what would be included if a subject continued on standard of care therapy. If there is a viable alternative you must list it in the consent.

The alternative is for research subjects not to participate.

Costs to Research Participants

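### As named, and with no missing-data method stated, the RMANOVA/RMANCOVA would test each outcome only in carers measured at T1, T2 and T3

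*Combined protocol and SAP*

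**What the plan says.** The Data Analysis Plan gives one inferential route for both aims: "For both study aims, we will use a 3 group by 3-time point Repeated Measures Analysis of Variance (RMANOVA", in two steps. In its words, "first, we will use RMANOVA to determine if mean differences exist among the 3 groups over 3 time points"; the RMANCOVA, with months in role, dementia symptom severity and caregiving demands as covariates, is run only if differences appear. Linear and quadratic contrasts over the three time points are added. There is no analysis set, no imputation and no rule for a carer with an incomplete outcome.

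Other sections bear on who will be incomplete:

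- **Study Design/Procedures, Consent.** Carers may withdraw, and are told that "they do not need to supply responses to all questions posed on the study questionnaires".
- **Study Design/Procedures, Data Collection.** If no remote option works, the data count as missed "if we cannot wait to collect the data in person at a later date".
- **Withdrawal of Research Participants.** Carers are withdrawn if "non-responsive to phone calls, emails, texts, or letters and considered lost to follow up". Nothing further is collected, but data gathered before "withdrawal will be de-identified and still be used in the data analysis for the study".
- **Provisions to Monitor the Data.** The safety committee reviews missing-data patterns and differential attrition. This is tied to no analysis.
- **Instrument table.** Of the Revised Memory and Behavior Problems Checklist, the Caregiver Appraisal of Functional Capacity and the care-recipient health rating it notes: "These scales will NOT be asked to caretakers". The Data Analysis Plan likewise tracks "dementia symptoms, level of care, and health rating of the care recipient for those who are not bereaved".

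**The concern.** A classical repeated-measures ANOVA on three time points needs all three values from each carer; the quadratic contrast cannot be formed without them. Complete-case deletion is therefore a consequence of the named method, although nobody wrote it as a rule.

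Randomisation comes after the T1 scales, so the carers removed are randomised people with baseline scores, and some also have T2 scores. Discarding them costs precision and power. It can also bias the comparison if the reason for leaving is related to T2 scores differently across arms. The stated intention to use pre-withdrawal data cannot be met by the stated tests; such data could enter only the descriptive statistics.

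The covariates narrow the set further. If the scales withheld from caretakers supply dementia severity and caregiving demands, as appears, the RMANCOVA contains no caretakers, even those seen three times.

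**Working it through.** The plan has no power, attrition or correlation figure to reproduce. Only the sample size of 350 comes from the documents (Number of Research Participants). Everything else below is an assumption: unit SD at each visit, equal arms of 350/3, loss a = 10% or 20% at each of T2 and T3 with no return, and correlation ρ = 0.6 between any two visits unless stated.

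**Who is left.** Complete: 350(1-a)². T1 and T2 only: 350(1-a)a. T1 only: 350a.

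| a | Complete | T1 and T2 only | T1 only |
|---|---|---|---|
| 10% | 283.5 | 31.5 | 35 |
| 20% | 224 | 56 | 70 |

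If the three phases were equal in size, an RMANCOVA without caretakers would start from 350 × 2/3 ≈ 233 carers before any attrition.

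**Precision under random loss.** The variances below are per arm, multiplied by the number randomised.

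- Complete-case, either change: 2(1-ρ)/(1-a)² = 0.8/0.81 = 0.988, or 0.8/0.64 = 1.250.
- Mixed model, T1 to T2: (1-ρ²)/(1-a) + (1-ρ)² = 0.64/0.9 + 0.16 = 0.871, or 0.64/0.8 + 0.16 = 0.960.
- Mixed model, T1 to T3: regressing T3 on T1 and T2 gives slopes 0.6/1.6 = 0.375 and residual variance 0.55. The variance is 0.55/(1-a)² + 0.375² × 0.64/(1-a) + 0.16 = 0.939, or 1.132.

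Square roots of the ratios give complete-case standard errors larger by factors of 1.065 and 1.141 for T1 to T2, and 1.026 and 1.051 for T1 to T3.

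**Planned group-by-time test.** For two arms (2 df), the information lost is 1.3% to 11.9% (a = 10%) or 2.6% to 23.4% (a = 20%), depending on the effect pattern. For an effect equal at T2 and T3 it is 10.3% or 20.4%.

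For three arms (4 df, chi-square approximation), with both active arms at effect vector e, the noncentrality is λ = (350/3) × (2/3) × e′We. W is the inverse of the covariance matrix of the two changes. For e = (-0.35, -0.35), complete-case λ = 116.67 × 0.6667 × 0.1225 × (2/1.2) × (1-a)² = 12.86 or 10.16; the mixed-model λ is 14.33 or 12.76.

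| Effect at T2, T3 | Power at a = 10%: mixed, complete-case | Power at a = 20%: mixed, complete-case |
|---|---|---|
| -0.35, -0.35 | 87.5%, 83.3% | 82.9%, 72.4% |
| -0.175, -0.35 | 72.5%, 69.8% | 63.6%, 58.1% |
| 0, -0.35 | 83.9%, 83.3% | 73.8%, 72.4% |

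**Bias.** Simulation with 1,000,000 carers per arm, a true effect of -0.35 (lower is better) and 20% dropout after T2. Dropout is random in control and depends on T2 in the active arm, with log-odds slopes of 0.4, 0.7 and 1.0 per SD.

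| Correlations | Who leaves the active arm | Complete-case T1 to T2 | Complete-case T1 to T3 |
|---|---|---|---|
| all 0.6 | worse scorers | -0.384, -0.399, -0.418 | -0.348 to -0.351 |
| all 0.6 | better scorers | -0.322, -0.298, -0.281 | -0.348 to -0.351 |
| T2-T3 0.75, others 0.5 | worse scorers | as far as -0.437 | -0.367, -0.383, -0.393 |
| T2-T3 0.75, others 0.5 | better scorers | as far as -0.265 | -0.329, -0.321, -0.308 |

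The pattern follows from regression on T2. Selection that shifts mean T2 by s moves the T1-to-T2 change by (1-ρ12)s and the T1-to-T3 change by (ρ23-ρ12)s. At slope 1.0 the first row implies s ≈ -0.068/0.4 = -0.17. With the unequal correlations this predicts -0.35 - 0.5 × 0.17 = -0.435 and -0.35 - 0.25 × 0.17 = -0.393, as simulated. T1 to T3 is therefore unbiased when T2 correlates equally with T1 and T3.

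With the same dropout mechanism in both arms (correlation 0.6, slopes 0.4 and 1.0), complete-case T1 to T2 is -0.346 and -0.336. With random dropout it is -0.350. The likelihood estimate stays within -0.346 to -0.354 in every scenario.

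**The case against.** The strongest reply is that deletion is inferred. RMANOVA names a group-by-time test; a long-format fit of a similar model could keep partial records, and the Objectives section speaks more broadly of repeated-measures bivariate and multivariate analyses. The document is an ethics-committee form and mentions a separate grant proposal, which may hold a missing-data plan. This is fair as to what the investigators intend, but neither the broad wording nor the form supplies a method here.

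Second, the withdrawal sentence concerns retention of data and is no analysis-set rule. It is in tension with the analysis plan rather than in flat contradiction. That stands, but the two still need reconciling.

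Third, the cost can be small. For an effect at T3 only, power falls by about 1 point or less, and T1-to-T3 standard errors rise by only 3% to 5% at correlation 0.6. The bias needs dropout that works differently by arm, which nothing in the documents predicts. Both points limit the size and leave the defect in place.

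Fourth, the caretaker covariates are a separate, structural problem: a mixed model alone does not cure it, the link from scales to covariates is inferred, and the RMANCOVA is only a conditional second step. This is correct, and the fix treats it separately. Confining two covariates to non-bereaved carers departs from the plan's statement that all analyses are adjusted, and makes the adjusted Aim 2 comparison one of two phases. If those scales are the covariates, the model as written could not have included caretakers anyway.

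**Conclusion.** The concern holds and should be fixed before analysis. It touches every outcome under both aims.

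The loss of precision needs only that some carers miss T2 or T3. Under the assumed 10% to 20% random loss per wave, the power cost across the effect patterns shown runs from under 1 to about 10 points. Bias is conditional: up to about 0.07 SD for T1 to T2 at correlation 0.6 when dropout depends on T2 in one arm only, in either direction. It is larger at lower correlation: at 0.4 the estimates run from -0.456 to -0.242. For T1 to T3 it is about 0.04 SD in the unequal-correlation case and nil when the T2 correlations are equal. If dropout is random or works alike in all arms, there is little or no bias. The loss of all caretakers from the RMANCOVA rests on the apparent, unstated match between the withheld scales and the two covariates.

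**What to change.** 1. For each outcome, make the primary analysis a likelihood-based linear mixed model with group, visit as a category, group-by-visit and an unstructured covariance. Include all carers with any score on that outcome; for Aim 1, all randomised carers as assigned. Keep the group-by-time test and the linear and quadratic contrasts. This also makes use of pre-withdrawal data, as the withdrawal section intends.
2. Fit that model without the scales not given to caretakers. Months in role may stay if it is recorded in all three phases. Use dementia severity and caregiving demands only in analyses of non-bereaved carers, and say that adjusted Aim 2 results then compare two phases.
3. State how a scale is scored when items are skipped.
4. Multiple imputation of missing outcome scores before the planned RMANOVA is an acceptable alternative. Scales that do not apply to the bereaved should not be imputed.
5. Both routes assume missing-at-random. Add one sensitivity analysis that departs from it, for example shifting unobserved T2 and T3 scores by arm.

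The cost is plan wording and some added analyst time, mainly for the sensitivity analysis across the outcomes. No new data or visits are needed, and the SPSS family named in the monitoring section can fit the model.
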